8.11.4.1 Ocular surface vital staining with Fluorescein (Oxford scale)

The scores of ocular surface vital staining with fluorescein and their changes from day 1 - pre-dose values and day 15±2 - pre-dose values for the study/primary eye and for the non-study/secondary eye will be listed ([Listing 16.2.6.2](#)) and summarised by treatment and time point using descriptive statistics (mean, SD, CV%, minimum, median and maximum) ([Table 14.2.1.2](#)).

The changes from day 1 - pre-dose values at day 15±2 pre-dose will be compared between treatments using a Student's t test ([Table 14.2.2.2](#)).

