1. STUDY SUMMARY

1.1 OVERALL STUDY SYNOPSIS

CLINICAL STUDY SYNOPSIS:
Study Number: LUB0116MD
Title of Study: A 2 week, randomized, double-masked, controlled, parallel group 1 week follow-up study to evaluate tolerability, safety, permanence on the ocular surface and efficacy of two concentrations of Lubricin (20 and 50 µg/mL) eye drops versus sodium hyaluronate (HA) 0.18% eye drops (Vismed®) in patients with ocular discomfort following refractive surgery.
Study Sites: 1 site in Italy
Phase of Development: pre-market
Study Objectives: The primary objective of the study is to assess the tolerability and safety of Lubricin (20 and 50 µg/mL) eye drops solution administered over 2 weeks in patients with ocular discomfort following refractive surgery. Secondary objectives of the study are aimed at studying efficacy, including ocular surface permanence, of Lubricin (20 and 50 µg/mL) eye drops solution administered over 2 weeks versus sodium hyaluronate (HA) 0.18% eye drops solution in patients with ocular discomfort following refractive surgery.
Study Design and Methodology: A 2 week randomized (1:1:1), controlled, double-masked, parallel group, pre-market study. Patients with ocular discomfort following refractive surgery procedure (within 6 months from enrollment into the investigation) will be evaluated at baseline (Day 1), at Week 2 (day 15±2 days) and at Week 3 follow-up visit (day 22±2, or early exit).
Number of Patients: Thirty (30) patients (10 per arm) randomized 1:1:1 to Lubricin 20 µg/ml eye drops solution or Lubricin 50 µg/ml eye drops solution or sodium hyaluronate (HA) 0.18% eye drops solution will be enrolled. As the primary objective of this study is to evaluate the tolerability and safety of Lubricin (20 and 50 µg/mL) eye drops solution administered over 2 weeks in patients with ocular discomfort following ocular refractive surgery, sample size was calculated based on clinical feasibility and no formal sample size calculation has been performed.

Diagnosis and Criteria for Inclusion/Exclusion:

Adult patients with ocular discomfort (defined as SANDE score ≥ 30 at baseline) following ocular refractive surgery (within 6 months from enrollment).

Inclusion Criteria:

1. Patients 18 years of age or older.
2. Patients undergone ocular refractive surgery within 6 months from Day 1 Visit.
3. Patients with ocular discomfort defined as SANDE score ≥ 30 at baseline.

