7.1.5 Analysis of Ophthalmological Evaluations

Variables will be presented using descriptive statistics according to the nature of the variable, i.e. arithmetic mean, SD, CV (%), minimum, median and maximum values for quantitative variables, proportions and frequencies for qualitative variables.

Considering the design of the study, data will be presented at Baseline, Day 15 and Follow-up periods separately. Changes from baseline and Day 15 will also be presented.

Inferential tests on changes from baseline will be used to estimate potential differences between treatments within Day 15 visits separately.

For the following variables Student t test will be considered:

Corneal fluorescein surface staining (Oxford score)

Schirmer's test (ST) I (without anaesthesia)

Tear Film Break Up Time (TFBUT)

Best corrected distance visual acuity (BCDVA)

Assessment of central corneal sensitivity by Cochet-Bonnet aesthesiometry

Symptom Assessment in Dry Eye (SANDE)

Intraocular pressure (IOP)

For Slit lamp examination (SLE), grading of the eyelids, lashes, conjunctiva, cornea, lens, iris and anterior chamber will be processed separately using Wilcoxon Rank Sum Test.

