1.1 Changes with respect to the investigational plan

The following changes were introduced into the SAP with respect to the clinical investigational plan (5):

- The tears collection for Lubricin dosing was insert as PK endpoint;
- The device deficiencies, external ocular examination, review of ocular medical condition and review of systemic medical condition were reported as safety and tolerability parameters.

These changes do not affect the principal features stated in the investigational plan and thus do not have to be documented in a protocol amendment.

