8.1 Tables, listings and figures layout

Tables, listings and figures will be provided according to the following settings:

- Background: White
- Foreground: Black
- Font face: Times
- Font style: Roman
- Font size: 10 pt
- Font weight: Medium (data, footers and notes), Bold (titles and headers)
- Font width: Normal
- Layout: Landscape
- Top Margin: 1.3 cm
- Bottom Margin: 1.3 cm
- Left Margin: 2 cm
- Right Margin: 2 cm
- Test labels: Lubricin 20 µg/mL, Lubricin 50 µg/mL
- Control label: Vismed® 0.18%
- Date format: ddMMMyyyy
- Means, standard deviations, percent coefficient of variations, medians, lower confidence limits and upper confidence limits will be rounded to one digit more than the original data
- Minima and maxima will keep the same number of decimal digits as the source values
- p-values will be rounded to the fourth decimal digit and will be flagged by an asterisk (*) in case of statistical significance (i.e. p-value < 0.05 or, in case of centre by treatment interaction, p-value < 0.10)
- p-values lower than 0.0001 will be reported as "<.0001 *".

The data and results of Lubricin 20 µg/mL and Lubricin 50 µg/mL will be presented before the data and results of Vismed® 0.18% in all listings and tables.

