8.3 Hypothesis tests

This is an exploratory investigation and no regulatory claim will be based on the results of this investigation.

The aim of the investigation is just to collect preliminary data in order to evaluate tolerability, safety, permanence on the ocular surface and efficacy of two concentrations of Lubricin (20 and 50 µg/mL) eye drops versus sodium hyaluronate (HA) 0.18% eye drops (Vismed®) in patients with ocular discomfort following refractive surgery.

No formal hypothesis test will be performed in order to compare the two concentrations of Lubricin (20 and 50 µg/mL) eye drops versus sodium hyaluronate (HA) 0.18% eye drops (Vismed®).

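### SAP 8.3 rules out formal Lubricin–Vismed tests, yet 8.11.4 plans them and 8.1 stars p < 0.05; the visible text names no arm pair or eye for the tests, and the t tests do not adjust for the Day 1 value

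*SAP*

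**What the plan says.** - SAP 8.3 calls the investigation exploratory, disclaims any regulatory claim, and adds "No formal hypothesis test will be performed in order to compare the two concentrations of Lubricin" with Vismed.
- SAP 8.11.4.1 (Oxford staining) says "The changes from day 1 - pre-dose values at day 15±2 pre-dose will be compared between treatments" using Student's t test. The same words recur in 8.11.4.2 to 8.11.4.8, except that 8.11.4.6 (slit lamp, 11 items) uses the Wilcoxon rank sum test.
- SAP 8.1 says p-values "will be flagged by an asterisk (*) in case of statistical significance", meaning below 0.05. The same rule has a threshold "in case of centre by treatment interaction", although the protocol synopsis gives "1 site in Italy".
- SAP 8.1 also says "lower confidence limits and upper confidence limits will be rounded to one digit more than the original data", but no visible sentence in 8.11.4 asks for a confidence interval.
- Protocol 7.1.5 says "Inferential tests on changes from baseline will be used to estimate potential differences between treatments within Day 15 visits separately".
- SAP 1.1 opens its list with "The following changes were introduced into the SAP with respect to the clinical investigational plan". It has two entries, and neither concerns 8.3.
- SAP 8.11.1.1 includes the Day 1 pre-dose value as a covariate in the VAS model. The t-tested endpoints have no such term.

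**The concern.** Read literally, 8.3 forbids what 8.11.4 plans and what 8.1 labels as significant. A reader of the report could not tell whether a starred p-value is a finding or a description.

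A t test compares two groups and the study has three arms. In the eye-level sections both eyes are named for listings and summaries, but the test sentence names none. The number of tests is therefore open, and could still be settled after unblinding.

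At 10 per arm a star may be chance, and a missing star may be read as similarity to Vismed. SAP 8.4 sets a precision only for VAS change and for the proportion with a TEAE, so none is stated for these endpoints. What is at stake is over-reading of exploratory results. Bias is not at issue: a t test on change is unbiased under randomization.

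**Working it through.** **The plan's own figure.** SAP 8.4.1: 2 × 10² × 1.96² / 9² = 9.49, rounded up to 10. SAP 8.4.2: 1.96² × (0.15 × 0.85 + 0.45 × 0.55) / 0.40² = 9.003, rounded up to 10. Both reproduce and neither is in dispute.

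**Number of tests.** The t-tested outcomes are Oxford, Schirmer, TFBUT, BCDVA, IOP and Cochet-Bonnet (six, by eye, with Cochet-Bonnet as one value) and SANDE frequency and intensity (two, by patient).
- Study eye, each Lubricin arm against Vismed: 8 × 2 = 16.
- Both eyes, all three pairs: (6 × 2 + 2) × 3 = 42. The text as written allows 16 to 42 t tests.
- Slit lamp, study eye, two pairs: 11 × 2 = 22.

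**Chance findings.** For the 16 comparisons, 0.05 × 16 = 0.8 expected. For the slit lamp, 0.05 × 22 = 1.1 at most, since tied grades seldom reject. The next table is a simulation with no true effect (10 per arm, r = 0.5, 20,000 runs), where r is the Day 1 to Day 15 correlation. It gives the probability of at least one result among the 16.

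| Correlation between outcomes (assumed) | Any t test p < 0.05 | Any ANCOVA interval excluding zero |
|---|---|---|
| 0 | 53.2% | 52.8% |
| 0.3 | 49.1% | 48.5% |
| 0.5 | 42.4% | 42.2% |

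**Precision, SANDE.** Protocol 3.2.1 gives an SD of 13 mm and 12 mm as the largest acceptable difference. The documents do not give r. With equal SDs on both days:
- SD of change = 13 × √(2(1 − r)), which is 13 mm at r = 0.5.
- Mean half-width of the t interval (18 df) = 2.101 × 13 × √(2/10) × 0.986 ≈ 12.0 mm. The factor 0.986 is the small-sample expectation of the SD.
- Variance ratio, ANCOVA to change score = (1 − r²) / (2(1 − r)) = (1 + r)/2 = 0.75 at r = 0.5.
- Allowing for chance baseline imbalance and 26 df, the width ratio is √(0.75 × 1.04) × 2.056/2.101 ≈ 0.864, and 12.0 × 0.864 ≈ 10.4 mm.

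Simulated mean 95% half-widths (20,000 runs, 10 per arm, equal SDs):

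| r (assumed) | t test on change | Three-arm ANCOVA | ANCOVA narrower by | ANCOVA wider in a single trial |
|---|---|---|---|---|
| 0.3 | 14.2 mm | 11.5 mm | 19% | 9% of runs |
| 0.5 | 12.0 mm | 10.4 mm | 13% | 16% |
| 0.7 | 9.3 mm | 8.6 mm | 8% | 26% |
| 0.9 | 5.4 mm | 5.3 mm | 2% | 39% |
| 0.95 | 3.8 mm | 3.8 mm | 1% | 43% |

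About 2 percentage points of each gain come from pooling the variance over three arms; at high r that is most or all of the gain. At r = 0.5 the t test would need about 13 per arm (10.4 mm) to match. At 9 per arm (the 10% drop-out of Protocol 7.3) the gains are unchanged: 19%, 13%, 8%, 2% and 1%. If the Day 1 SD is 0.75 of the Day 15 SD, the gains are 10%, 4%, 0% and 5% at r = 0.3, 0.5, 0.7 and 0.9, and ANCOVA is wider in 23%, 36%, 46% and 32% of runs.

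**What a missing star leaves open.** A non-significant estimate can lie almost one half-width from zero, so its interval can reach almost two. The 12 mm can therefore stay inside whenever the half-width exceeds about 12/2 = 6 mm. With equal SDs this is so for the t test at r = 0.3, 0.5 and 0.7, but not at 0.9.

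**The case against.** The strongest reply is that 8.3 opens by calling the study exploratory, so its denial of formal tests naturally means no confirmatory tests. On that reading the tests in 8.11.4 simply carry out Protocol 7.1.5, and SAP 1.1 had nothing to list. SAP 8.4 also disclaims multiplicity adjustment, though only for confidence intervals. This reading is plausible, but 8.3 does not say it, no test sentence in 8.11.4 calls its test exploratory, and 8.1 calls p < 0.05 statistical significance. The asterisk rule looks like generic text, which explains it without removing the conflict.

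Second, pair, eye and intervals may be set out in redacted table shells. The secondary objective and 8.4.2 point to each Lubricin arm against Vismed, and the confidence-limit rounding in 8.1 suggests that intervals were expected. This stands as a limit: the gap is in the visible text only.

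Third, ANCOVA is a choice of efficiency, and the protocol specified the t test. The gain is small at high r and almost nil at some SD ratios. The SANDE entry threshold of 30 may well shrink the Day 1 SD. All of that stands. The change is still cheap, and it follows the SAP's own VAS model.

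Fourth, the match with 12 mm depends on r and on figures from another population, regimen and comparator, for the overall score. The exact match does depend on r = 0.5, or on reading 13 mm as the SD of change. The wider point needs only a half-width above about 6 mm.

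Last, ANCOVA intervals exclude zero by chance as often as the t tests do. This is correct.

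**Conclusion.** The concern holds. SAP 8.3, 8.1 and 8.11.4 do not fit together, and the visible text leaves 16 to 42 possible t tests. Under the smallest of these counts, about 0.8 chance stars are expected and the probability of at least one is 42% to 53%. SANDE comparisons are accurate to about ±12 mm at r = 0.5, with a range of ±14.2 to ±3.8 mm over r = 0.3 to 0.95. Baseline adjustment narrows this by 13% on average at r = 0.5, and by 1% to 19% over that range.

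The figures assume values for r, for the SD ratio and for the correlation between outcomes. They also carry the overall-score SD of 13 mm from an earlier study in moderate dry eye over to each SANDE item here. The conflict between sections, and the missing pair and eye in the visible text, need no such assumption.

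Unadjusted p-values are acceptable in a declared exploratory study, so the weight is minor to moderate, but the text should be corrected before database lock. Two secondary items lie outside these tests and are not resolved here: Lubricin concentrations are only listed (8.10), and SANDE improvement speed has no defined analysis.

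**What to change.** 1. For the t-tested endpoints in 8.11.4, fit one three-arm ANCOVA: Day 15 pre-dose value on treatment and Day 1 pre-dose value, in the study eye of 8.6, with SANDE per patient. Report each Lubricin arm minus Vismed with a 95% confidence interval. Keep the non-study eye descriptive. If the redacted shells already name pair and eye, make the text match them.
2. Delete the asterisk rule in 8.1. Reword 8.3 to say that no confirmatory test is made and that all p-values and intervals are exploratory and unadjusted for multiplicity.
3. State beside the results that 16 comparisons are made and that about 0.8 would exclude zero by chance. Keep the slit-lamp Wilcoxon tests under the same label, with their count of 22.
4. List the departure from Protocol 7.1.5 in SAP 1.1.

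The cost is SAP wording, one line in 1.1 and changes to table shells; no new data are needed. The baseline slope uses one degree of freedom, and the interval can be wider in a single trial. A linear model is only approximate for Oxford grades and for Cochet-Bonnet lengths (0.5 cm steps, maximum 6 cm). Dropping the asterisks also changes the VAS table (14.2.2.1). None of this controls multiplicity; step 3 only makes the chance rate visible.

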8.11.4.2 Schirmer-I test (without anaesthesia)

The values of 8.8.4.2 Schirmer-I test (without anaesthesia) and their changes from day 1 - pre-dose values and day 15±2 - pre-dose values for the study/primary eye and for the non-study/secondary eye will be listed ([Listing 16.2.6.3](#)) and summarised by treatment and time point using descriptive statistics (mean, SD, CV%, minimum, median and maximum) ([Table 14.2.1.3](#)).

The changes from day 1 - pre-dose values at day 15±2 pre-dose will be compared between treatments using a Student's t test ([Table 14.2.2.3](#)).

8.11.4.3 Tear film break-up time

The values of tear film break-up time and their changes from day 1 - pre-dose values and day 15±2 - pre-dose values for the study/primary eye and for the non-study/secondary eye will be listed ([Listing 16.2.6.4](#)) and summarised by treatment and time point using descriptive statistics (mean, SD, CV%, minimum, median and maximum) ([Table 14.2.1.4](#)).

The changes from day 1 - pre-dose values at day 15±2 pre-dose will be compared between treatments using a Student's t test ([Table 14.2.2.4](#)).

8.11.4.4 Best corrected distance visual acuity

The values of best corrected distance visual acuity and their changes from day 1 - pre-dose values and day 15±2 - pre-dose values for the study/primary eye and for the non-study/secondary eye will be listed ([Listing 16.2.6.5](#)) and summarised by treatment and time point using descriptive statistics (mean, SD, CV%, minimum, median and maximum) ([Table 14.2.1.5](#)).

The changes from day 1 - pre-dose values at day 15±2 pre-dose will be compared between treatments using a Student's t test ([Table 14.2.2.5](#)).

8.11.4.5 Symptom assessment in dry eye

The values of symptom assessment in dry eye (frequency of symptoms and intensity of symptoms) and their changes from day 1 - pre-dose values and day 15±2 - pre-dose values will be listed ([Listing 16.2.6.6](#)) and summarised by treatment and time point using descriptive statistics (mean, SD, CV%, minimum, median and maximum) ([Table 14.2.1.6](#)).

The changes from day 1 - pre-dose values at day 15±2 pre-dose will be compared between treatments using a Student's t test ([Table 14.2.2.6](#)).

8.11.4.6 Slit lamp examination

The scores of slit lamp examination (Eyelid - Meibomian glands, Eyelid - Erythema, Eyelid - Oedema, Lashes, Conjunctiva - Erythema, Conjunctiva - Oedema, Lens, Iris, Anterior Chamber Inflammation, Cornea transparency and Cornea neovascularization) and their changes from day 1 - pre-dose values and day 15±2 - pre-dose values for the study/primary eye and for the non-study/secondary eye will be listed ([Listing 16.2.6.7](#)) and summarised by treatment and time point using descriptive statistics (mean, SD, CV%, minimum, median and maximum) ([Table 14.2.1.7](#)).

The changes from day 1 - pre-dose values at day 15±2 pre-dose will be compared between treatments using a Wilcoxon Rank Sum Test ([Table 14.2.2.7](#)).

8.11.4.7 Intraocular pressure

The values of intraocular pressure and their changes from day 1 - pre-dose values and day 15±2 - pre-dose values for the study/primary eye and for the non-study/secondary eye will be listed ([Listing 16.2.6.8](#)) and summarised by treatment and time point using descriptive statistics (mean, SD, CV%, minimum, median and maximum) ([Table 14.2.1.8](#)).

The changes from day 1 - pre-dose values at day 15±2 pre-dose will be compared between treatments using a Student's t test ([Table 14.2.2.8](#)).

8.11.4.8 Corneal sensitivity by Cochet-Bonnet aesthesiometry

The values of corneal sensitivity by Cochet-Bonnet aesthesiometry and their changes from day 1 - pre-dose values and day 15±2 - pre-dose values for the study/primary eye and for the non-study/secondary eye will be listed ([Listing 16.2.6.9](#)) and summarised by treatment and time point using descriptive statistics (mean, SD, CV%, minimum, median and maximum) ([Table 14.2.1.9](#)).

The changes from day 1 - pre-dose values at day 15±2 pre-dose will be compared between treatments using a Student's t test ([Table 14.2.2.9](#)).

8.11.5 Interim analyses

No interim analysis is planned.

8.12 Safety and tolerability analysis

The safety and tolerability analysis will be performed on the subjects included into the Safety Set.

Subjects will be analysed according to the treatment they actually received.

8.12.1 Adverse events

Adverse events (AEs) will be coded by System Organ Class (SOC) and Preferred Term (PT), using the Medical Dictionary for Regulatory Activities (MedDRA) version 20.1.

AEs will be classified as pre-treatment AEs (PTAEs) and treatment-emergent AEs (TEAEs), according to the period of occurrence, as follows:

- PTAEs: all AEs occurring before the first dose of the ID and not worsening after the first dose of the ID
- TEAEs: all AEs occurring or worsening after the first dose of the ID

Individual PTAEs and TEAEs will be listed by treatment ([Listing 16.2.7.1](#), [Listing 16.2.7.2](#)).

No summary table will be provided for PTAEs.

TEAEs will be summarised by treatment and overall.

- The number and percentage of subjects with any TEAE and the number of TEAEs will be presented overall ([Table 14.3.1.1](#)) and by SOC and PT ([Table 14.3.1.2](#));
- The number and percentage of subjects with any TEAE by relationship and the number of TEAEs by relationship will be presented ([Table 14.3.1.1](#));
- The number and percentage of subjects with any TEAE by intensity and the number of TEAEs by intensity will be presented overall ([Table 14.3.1.1](#)) and by SOC and PT ([Table 14.3.1.3](#));
- The number and percentage of subjects with any TEAE related to the ID ([Table 14.3.1.1](#)) and the number of TEAEs related to the ID will be presented overall and by SOC and PT ([Table 14.3.1.4](#));
- The number and percentage of subjects with any TEAE leading to discontinuation and the number of TEAEs leading to discontinuation will be presented ([Table 14.3.1.1](#)).

Serious TEAEs will be summarised by treatment and overall.

- The number and percentage of subjects with any Serious TEAE and the number of Serious TEAEs will be presented overall ([Table 14.3.1.1](#)) and by SOC and PT ([Table 14.3.1.5](#));
- The number and percentage of subjects with any Serious TEAE by relationship and the number of Serious TEAEs by relationship will be presented ([Table 14.3.1.1](#));
- The number and percentage of subjects with any Serious TEAE related to the ID and the number of Serious TEAEs related to the ID will be presented overall and by SOC and PT ([Table 14.3.1.6](#));
- The number and percentage of subjects with any Serious TEAE leading to discontinuation and the number of Serious TEAEs leading to discontinuation will be presented ([Table 14.3.1.1](#)).

All TEAEs leading to death will be listed, all Serious TEAEs will be listed and all TEAEs leading to discontinuation will be listed ([Table 14.3.2.1](#)).

8.12.2 Device deficiencies

The record dates and the descriptions of the device deficiencies will be listed by treatment ([Listing 16.2.7.3](#)).

8.12.3 External ocular examination

The date of external ocular examination, the overall investigator's interpretation (Normal; Abnormal, Not Clinically Significant; Abnormal, Clinically Significant) and clinically significant abnormalities (if any) for the study/primary eye and for the non-study/secondary eye will be listed by treatment and time point ([Listing 16.2.9.1](#)).

8.12.4 Review of ocular medical condition

The date of review ocular medical condition, the overall investigator's interpretation (Normal; Abnormal, Not Clinically Significant; Abnormal, Clinically Significant) and clinically significant abnormalities (if any) will be listed by treatment and time point ([Listing 16.2.9.2](#)).

8.12.5 Review of systemic medical condition

The date of review systemic medical condition, the overall investigator's interpretation (Normal; Abnormal, Not Clinically Significant; Abnormal, Clinically Significant) and clinically significant abnormalities (if any) will be listed by treatment and time point ([Listing 16.2.9.3](#)).

